6.1.1 Primary Efficacy Endpoint

There are two separate regionally based primary efficacy endpoints in this study depending upon whether the data are being filed to support submission to the EU EMA or to ex-EU health authorities, such as the US FDA.

6.1.1.1 Primary Efficacy Endpoint for EU (EMA)

The primary efficacy endpoint is a binary variable, Hb response (Yes/No), where Yes is defined as:

- Hb ≥ 11.0 g/dL and Hb increase from baseline by ≥ 1.0 g/dL, for subjects with baseline Hb > 8.0 g/dL; or
- Hb increase from baseline by ≥ 2.0 g/dL, for subjects with baseline Hb ≤ 8.0 g/dL

at two consecutive visits [dates] (with available data) separated at least 5 days during the first 24 weeks of treatment without having received rescue therapy (RBC transfusion, ESA, or IV iron) prior to Hb response.

Both scheduled and unscheduled Hb values from the central laboratory will be taken into account.

The first date of the two consecutive visits will be used as the date of response. Analysis visits will be used to define the week of response (see [Table 31](#), Section [7.11.4](#)).

Subjects who discontinued or received rescue therapy prior to the first Hb that fulfills the definition of response or before the second consecutive Hb value that fulfills the definition of response, will be classified as non-responders.

Baseline Hb is defined as the mean of four central laboratory Hb values: four latest Hb values prior or on the same date as first study drug intake (pre-dose).

Definition of rescue therapy is provided in Section [6.1.2.3](#)

6.1.1.2 Primary Efficacy Endpoint for US (FDA)

Hb change from baseline (BL) to the average Hb of weeks 28 to 52 regardless of rescue therapy.

The central laboratory reported Hb values will be used for this analysis.

All available Hb values obtained from the central laboratory will be used (i.e., both scheduled and unscheduled Hb values). Hb values in analysis visit windows at weeks 28, 32, 36, 40, 44, 48 and 52 will be used for the calculation of the average of weeks 28 to 52 (see [Table 31](#) and Section [7.11.4](#) for the analysis windows definition and the differentiation between the MMRM and ANCOVA analyses).

In case a subject does not have any available Hb value within this evaluation period refer to Section 7.11.1 for imputation rules.

Baseline Hb is defined as the mean of four central laboratory Hb values: four latest Hb values prior or on the same date as first study drug intake.

6.1.2 Key Secondary Efficacy Endpoints

The key secondary efficacy endpoints in this study are listed in Table 4

Table 4 Key Secondary Efficacy Endpoints

Number	Endpoint
1	Hb change from BL to the average Hb in weeks 28-36, without having received rescue therapy within 6 weeks prior to and during this 8-week evaluation period.
2	Change from BL in Low Density Lipoprotein (LDL) cholesterol to the average LDL cholesterol of weeks 12 to 28.
3	Occurrence and time to first use of rescue therapy [composite of RBC transfusions, IV iron supplementation and rescue ESA]
4	Change from BL in SF-36 Vitality (VT) sub-score to the average VT sub-score of weeks 12 to 28.
5	Change from BL in SF-36 Physical Functioning (PF) sub-score to the average PF sub-score of weeks 12 to 28.
6*	Change from BL in mean arterial pressure (MAP) to the average MAP value of weeks 20 to 28.
7*	Occurrence and time to first occurrence of hypertension (defined as either SBP \geq 170 mmHg AND an increase from BL \geq 20 mmHg or as DBP \geq 110 mmHg, AND an increase from BL of \geq 15 mmHg)
8*	Rate of progression of CKD measured by annualized eGFR slope over time

*: These key secondary endpoints will not be included in the hierarchical testing procedure.

6.1.2.1 Hb change from BL to the average Hb in weeks 28-36, without having received rescue therapy within 6 weeks prior to and during this 8-week evaluation period

All available Hb values obtained from the central laboratory will be used (i.e., both scheduled and unscheduled Hb values). Hb values in analysis visit windows at weeks 28, 32 and 36 will be used for the calculation of the average of weeks 28 to 36 (see Table 31 and Section 7.11.4 for the analysis windows definition and the differentiation between the MMRM and ANCOVA analyses).

In case a subject does not have any available Hb value within this evaluation period, or in case a subject requires rescue therapy within 6 weeks prior to and during this 8-week evaluation period, refer to Section 7.11.1 for imputation rules.

Baseline Hb is defined in Section 6.1.1.1

6.1.2.2 Change from BL in Low Density Lipoprotein (LDL) Cholesterol to the Average LDL Cholesterol of Weeks 12 to 28

The analysis will be done on all values (fasted and non fasted) of Day 1 and weeks 12 to 28.

All available LDL values will be used (regardless the fasting status), i.e., both scheduled and unscheduled LDL values. LDL values in analysis visit windows at weeks 12, 20 and 28 will

be selected for the calculation of the average LDL cholesterol of weeks 12-28 (see [Table 33](#) and Section [7.11.4](#) for the analysis windows definition and the differentiation between the MMRM and ANCOVA analyses).

For missing LDL imputation rules, refer to Section [7.11.1](#). Baseline LDL is defined as the LDL value on Day 1. If this value is missing, the latest value prior to first study drug administration will be used.

This analysis will also be repeated for fasted values only as a sensitivity analysis.

6.1.2.3 Use and time to first use of rescue therapy (composite of RBC transfusions, ESA use, and IV iron)

RBC transfusion is collected in the Blood Transfusions form of the eCRF. The use of ESAs and IV iron is collected in the Concomitant Medication form of the eCRF (entries where “Given as Anemia Therapy?” is ticked). These medications will be coded into the ATC and WHO-DRL dictionaries.

The following WHO-DRL codes will be classified as ESA: '00909301001', '00928301001', '02198701001', '07973701001', '01703101001'. The following WHO-DRL code where route is INTRAVENOUS will be classified as IV IRON: '00023501001' and '90135401001'. The following WHO-DRL code will be classified as RBC transfusion: '01186901001'.

Only rescue medication that started during the study treatment and up to the end of Efficacy Emergent Period will be taken into account and considered as use of rescue. Medication started at End of Treatment visit will not be considered rescue for patients completed the treatment. Medication Onset Date is the date of the first use of rescue medication.

For a subject with use of rescue therapy, the time to use of rescue therapy will be calculated (in years) as:

$$(\text{First event date} - \text{Analysis date of first dose intake} + 1) / 365.25$$

With ‘First event date’ defined as ‘Date of first dose of rescue medication’ during the Efficacy Emergent Period and ‘Analysis date of first dose intake’ defined in Section [6.5.4](#)

For a subject without use of rescue therapy, the time to censoring is calculated as:

$$[(\text{Date of End of Efficacy Emergent Period} - \text{Analysis date of first dose intake} + 1) / 365.25$$

With date of End of Efficacy Emergent Period defined in Section [7.11.6](#)

6.1.2.4 Change from BL in SF-36 Vitality (VT) Sub-score to the Average VT Sub-score of Weeks 12 to 28

For details on the calculation of the SF-36 VT scale subscore, see Section [6.1.3.14.1](#)

All available SF-36 VT values will be used i.e., both scheduled and unscheduled SF-36 VT values. SF-36 PF values in analysis visit windows at weeks 12 and 28 will be selected for the calculation of the average VT sub-score of weeks 12 to 28 (see [Table 32](#) and Section [7.11.4](#) for the analysis windows definition and the differentiation between the MMRM and ANCOVA analyses).

For missing SF-36 VT, refer to Section [7.11.1](#) for the imputation rules. Baseline assessment is the assessment from Day 1 visit.

6.1.2.5 Change from BL in SF-36 Physical Functioning (PF) Sub-score to the Average PF Sub-score of Weeks 12 to 28

For details on the SF-36 PF subscore, refer to Section [6.1.3.14.1](#). Similar rules as for Section [6.1.2.4](#) will be used for the calculation of the SF-36 VT scale sub-score.

6.1.2.6 Change from BL in Mean Arterial Pressure (MAP) to the Average MAP Value of Weeks 20 to 28

Blood pressure will be measured singly for the three visits during the screening period and in triplicate with a 2-minute interval for all other visits during the study. During the study, for systolic blood pressure (SBP) and diastolic blood pressure (DBP), the average will be calculated for each visit using the three readings. If less than three readings are available, all will be used in the calculation of the average.

MAP will be derived for each visit from the above averaged SBP and the DBP using the following equation:

$$\text{MAP} = (2/3) * \text{DBP} + (1/3) * \text{SBP}$$

All available MAP values during the Safety Emergent Period will be used, i.e. both scheduled and unscheduled MAP values. MAP values in analysis visit windows at weeks 20, 22, 24 and 28 will be selected for the calculation of the average MAP during weeks 20-28 (see [Table 31](#) and Section [7.11.4](#) for the analysis windows definition and the differentiation between the MMRM and ANCOVA analyses).

For missing data imputation rules, refer to Section [7.11.1](#). Baseline assessment is the assessment on Day 1 (average of the three readings). If the baseline assessment is missing, then the latest available value prior to first drug administration will be used.

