7.4.2 Secondary Endpoints

7.4.2.1 Primary Analysis

Once the primary hypothesis has been rejected for the EU (EMA) primary efficacy endpoint [see Section 7.4.1.1], the key secondary endpoints below will be tested using a fixed sequence testing procedure, as depicted in Table 9, in order to maintain the overall 2-sided type I error rate at 0.05. If P-value from a test is < 0.05 , the claim of superiority (or noninferiority for tests 6 and 7) will be considered successful and the test will progress to the next comparison in sequence. The analysis set for the analysis of the secondary endpoints will be the PPS for the noninferiority tests and the FAS for the superiority tests.

Table 9 Secondary Endpoints Fixed Sequence Testing Procedure

Test	Endpoint	Test (superiority unless otherwise specified)
1	Hb change from BL	*Pooled roxadustat versus pooled placebo
2	LDL change from BL	*Pooled roxadustat versus pooled placebo
3	Use and time to use of rescue therapy	*Pooled roxadustat versus pooled placebo
4	SF-36 PF subscore change from BL	*Pooled roxadustat versus pooled placebo
5	SF-36 vitality subscore change from BL	*Pooled roxadustat versus pooled placebo
6	MAP change from BL	Noninferiority of pooled roxadustat versus pooled placebo
7	Occurrence and time to occurrence of hypertension	Noninferiority of pooled roxadustat versus pooled placebo

*Subjects randomized to roxadustat QW, BIW and TIW prior to implementation of protocol v2.0 will be pooled together. Subjects randomized to placebo will also be pooled together.

- Change from BL in the average Hb of weeks 28-36, without having received rescue therapy within 6 weeks prior to and during this 8-week evaluation period (superiority of pooled roxadustat versus pooled placebo) will be analyzed using a MMRM with unstructured covariance matrix model. The model will contain terms for treatment arm, BL measurement, visit, visit x treatment arm and other stratification factors.
- Change from BL in LDL cholesterol to the average value of LDL cholesterol of weeks 12-28 will be compared (superiority of pooled roxadustat versus pooled placebo) using a MMRM model with unstructured covariance containing terms for treatment arm, BL measurement, visit, visit x treatment arm, and other stratification factors.

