- Use and time to use of rescue therapy (composite of RBC transfusion, ESA use and IV iron) in the first 24 weeks of treatment will be reported and compared using stratified Cox Proportional Hazards regression adjusting for stratification factors. Hazard ratio and its 95% will be calculated for the frequency of pooled roxadustat as relative to pooled placebo. Superiority will be declared if the lower bound of the 2-sided 95% CI is higher than 1.0.
- Change from BL in SF-36 PF subscore to the average in weeks 12-28 will be compared (superiority of pooled roxadustat versus pooled placebo) for all subjects and in the subset of subjects with BL PF subscore below 35, using a MMRM model with unstructured covariance containing terms for treatment arm, BL measurement, visit, visit x treatment arm, and other stratification factors.
- Change from BL in SF-36 vitality subscore to the average SF-36 vitality subscore in weeks 12-28 will be compared (superiority of pooled roxadustat versus pooled placebo) for all subjects and in the subset of subjects with BL vitality subscore below 50, using a MMRM model with unstructured covariance containing terms for treatment arm, BL measurement, visit, visit x treatment arm, and other stratification factors.

- Change from BL in MAP to the average MAP in weeks 20–28 will be compared (noninferiority of pooled roxadustat versus pooled placebo) using a MMRM model with unstructured covariance containing terms for treatment arm, BL measurement, visit, visit x treatment arm, and other stratification factors. Noninferiority will be declared if the upper bound of the 2-sided 95% CI of the difference between roxadustat and placebo is below 2 mmHg.
- Occurrence and time to occurrence of hypertension will be reported and compared (noninferiority of pooled roxadustat versus pooled placebo) using stratified Cox Proportional Hazards regression adjusting for stratification factors. Hazard ratio and its 95% will be calculated for the frequency of pooled roxadustat as relative to pooled placebo. Noninferiority will be declared if the upper bound of the 2-sided 95% CI does not exceed 1.3. Once this hypothesis is rejected, superiority will be checked but not as part of the sequence testing procedure.

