*: These key secondary endpoints will not be included in the hierarchical testing procedure.

No multiplicity adjustment will be done for the last three endpoints. Details of the analysis for each of these secondary endpoints are given below.

7.4.2.1 Hb change from baseline to the average Hb in weeks 28-36, without having received rescue therapy within 6 weeks prior to and during this 8-week evaluation period

Hb change from baseline to the average Hb value in weeks 28-36 will be compared by treatment arms using a MMRM model as in Section [7.4.1.2](#)

The analysis will be similar to the analysis provided in Section [7.4.1.2](#) except that evaluation period will be from baseline to weeks 28-36, without having received rescue therapy within 6 weeks prior to and during this 8-week evaluation period.

The analysis will be done on the FAS.

This superiority test will be considered successful if the lower bound of the two-sided 95% confidence interval of the difference between treatment arms (roxadustat minus placebo) is higher than 0.

An additional analysis (not part of the sequence) will be done for this endpoint on the FAS regardless the use of rescue therapy, as detailed in [Table 17](#)

Table 17 Primary and sensitivity analysis for the Hb change from BL to the average Hb in weeks 28-36

Code	Set	Rescue Therapy	Endpoint	Method	Covariates
Primary	FAS	Without rescue therapy	Change to the Average Hb in weeks 28-36	MMRM	Region, History of CV, visits and visits by treatment as categorical variables. BL Hb and BL eGFR as continuous covariates.
S1	FAS	Regardless rescue therapy	Change to the Average Hb in weeks 28-36	MMRM	Region, History of CV, visits and visits by treatment as categorical variables. BL Hb and BL eGFR as continuous covariates.

7.4.2.2 Change from BL in Low Density Lipoprotein (LDL) cholesterol to the average LDL cholesterol of weeks 12 to 28

LDL change from baseline to the average LDL value in weeks 12-28 will be compared by treatment arms using a MMRM model as in Section [7.4.1.2](#) (with the addition of LDL at baseline as continuous covariate). The analysis will be done on the FAS.

The analysis will be similar to the analysis provided in Section [7.4.1.2](#). This superiority test will be considered successful if the upper bound of the two-sided 95% confidence interval of the difference between treatment arms (roxadustat minus placebo) is below 0.

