7.4.2.6 Change from BL in mean arterial pressure (MAP) to the average MAP value of weeks 20 to 28

The blood pressure effect is shown by use of the change from baseline in MAP.

MAP change from baseline to the average MAP value in weeks 20-28 will be analyzed using a MMRM model as in Section 7.4.1.2.1 (with the addition of MAP at baseline as continuous covariate) . The analysis will be done on the PPS.

For missing MAP imputation rules, refer to Section 7.11.1

Non-inferiority can be concluded if the upper bound of the two-sided 95% CI of the difference between roxadustat and placebo (roxadustat minus placebo), calculated on the PPS is below 2 mm Hg.

An additional analysis (not part of the sequence) will be done on the All Randomized.

Table 22 Primary and sensitivity analysis for the MAP change from BL to the average MAP in weeks 20-28

Code	Set	Endpoint	Method	Covariates
Primary	PPS	Change from baseline to the Average MAP in weeks 20-28	MMRM	Region, History of CV, visits and visits by treatment as categorical variables. BL MAP, BL Hb and BL eGFR as continuous covariates.
S1	All Randomized	Change from baseline to the Average MAP in weeks 20-28	MMRM	Region, History of CV, visits and visits by treatment as categorical variables. BL MAP, BL Hb and BL eGFR as continuous covariates.

In addition to the inferential analyses, MAP and MAP change from baseline will be reported descriptively by visit, using all available data. The average of weeks 20-28 will also be reported.

Residual plots will be produced showing the following:

- Model residuals in the y-axis and model predictions in the x-axis,
- Model residuals in the y-axis and baseline MAP in the x-axis.

7.4.2.7 Time to first occurrence of hypertension (defined as either SBP ≥170 mmHg AND an increase from BL ≥ 20 mmHg or as DBP ≥ 110 mmHg, AND an increase from BL ≥ 15 mmHg)

Time to first occurrence of an increase in blood pressure, including time to censoring, defined in Section [6.1.2.7](#) will be used in a Cox Proportional Hazards regression analysis, to compare treatment arms, stratified for region and history of CV and adjusted for baseline eGFR and baseline Hb (both continuous), and provide hazard ratio and their 95% confidence intervals.

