7.4.2.8 Rate of progression of CKD measured by annualized eGFR slope over time

Geometric Mean (GM) and coefficient of variation (CV) will be displayed for eGFR. In addition, change from baseline and 95% CI will be presented.

The annualized eGFR slope over time (expressed in ml/min per 1.73 m² or % per year) will be determined using the SAS code below:

```
proc mixed data=egfr2;
class usubjid strata_except_egfr_hb TRTPN TRTP;
model aval= strata_except_egfr_hb HGBBL atptn
HGBBL*atptn egfrbl*atptn atptn*TRTPN*TRTP
atptn*strata_except_egfr_Hb / solution ddfm=kr
outpredm=pred cl;
random intercept atptn / subject=usubjid type=un ;
estimate 'Annualized slope Roxadustat'
intercept 0
strata_except_egfr_hb 0 0 0 0
HGBBL 0
atptn 1
HGBBL*atptn &meanHbBase
egfrbl*atptn &mean egfrbl
atptn*TRTPN*TRTP 1 0
atptn*strata_except_egfr_Hb &prop_strata
/cl;
estimate 'Annualized slope Placebo'
intercept 0
strata_except_egfr_hb 0 0 0 0
HGBBL 0
atptn 1
HGBBL*atptn &meanHbBase
egfrbl*atptn &mean egfrbl
atptn*TRTPN*TRTP 0 1
atptn*strata_except_egfr_Hb &prop_strata
/cl;
ods output lsmeans=lsmeans_un estimates=est_un;
ods output FitStatistics=FitStatistics SolutionF=SolutionF;
run;
```

Annualized eGFR slope over time is estimated by a random slopes and intercepts model using all available eGFR values (one baseline and all post-treatment values up to End of Treatment Period or start of dialysis) adjusted on Baseline Hb, Region, CV history at

Baseline and the interaction terms (Baseline eGFR by timepoint and Baseline Hb by timepoint). All assessments collected after initiation of acute or chronic dialysis will be excluded from the analysis.

Superiority will be declared if the lower bound of the two-sided 95% confidence interval of the difference in Least Square Means between roxadustat and placebo is above 0.

Model checking:

Residual plots will be produced showing the following:

- Model residuals in the y-axis and model predictions in the x-axis,
- Model residuals in the y-axis and baseline Hb in the x-axis.

Different dot styles will be used for the two treatment arms. Solid black symbols (square) will be used for roxadustat and non-solid red symbols (X) will be used for placebo.

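### The SAP moves MAP and hypertension noninferiority outside the protocol's fixed sequence and adds eGFR slope outside it, yet keeps success rules for all three, so three of eight key secondary claims lack familywise error control

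*SAP*

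**What the plan says.** **Protocol.** Section 7.4.2.1 tests the key secondary endpoints one after another once the EU primary hypothesis is rejected, "in order to maintain the overall 2-sided type I error rate at 0.05". Table 9 lists seven tests. MAP noninferiority is test 6 and hypertension noninferiority is test 7, and the text confirms that they belong to the procedure: "If P-value from a test is < 0.05 , the claim of superiority (or noninferiority for tests 6 and 7) will be considered successful". The synopsis gives them the same positions. On hypertension superiority the protocol says that "superiority will be checked but not as part of the sequence testing procedure". The eGFR slope is not a key secondary endpoint in protocol 2.3.2; it appears among the additional ones in 2.3.3.1.

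**SAP.** Tables 4 and 16 list eight key secondary endpoints. MAP (6), hypertension (7) and eGFR slope (8) carry a star explained as "These key secondary endpoints will not be included in the hierarchical testing procedure". Below Table 16 the SAP adds "No multiplicity adjustment will be done for the last three endpoints".

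The three endpoints still have success rules:
- MAP (7.4.2.6): "Non-inferiority can be concluded if the upper bound of the two-sided 95% CI" of the difference is below 2 mmHg.
- Hypertension (7.4.2.7): noninferiority is declared if the upper 95% bound of the hazard ratio is below 1.3.
- eGFR slope (7.4.2.8): "Superiority will be declared if the lower bound of the two-sided 95% confidence interval" of the difference is above 0.

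**The concern.** The protocol allows a blood pressure noninferiority claim only after the EU primary and tests 1 to 5 have all succeeded. On the SAP's tables, the same claim does not depend on tests 1 to 5. If, say, the LDL or an SF-36 test failed, the protocol would bar a MAP or hypertension claim and the SAP tables would permit one. The eGFR slope, a superiority claim that the protocol does not rank as key secondary, gets the same treatment.

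The SAP is also not consistent within itself:
- Section 7.4.2 still describes a successful noninferiority claim as moving the procedure on to the next test, although no noninferiority test is left in the sequence.
- Section 7.4.2.6 describes only the extra MAP analysis on all randomized subjects as outside the sequence, which implies that the per-protocol MAP test is inside it.
- Section 7.4.2.7 cites Table 16 for checking hypertension superiority within the fixed sequence. The Table 16 footnote and the protocol both put that check outside.

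Two statisticians could program different decision rules from this SAP and each point to text in support. The SAP's revision history does not settle the matter. It records a new ordering of the key secondary endpoints, the exchange of SF-36 Vitality and Physical Functioning, and the addition of eGFR slope, but not the removal of MAP and hypertension from the sequence.

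**Working it through.** **Inputs**
- Overall level of the sequence: 0.05 two-sided (protocol 7.4.2.1; SAP 7.4.2). Counted in roxadustat's favour only, this is 0.025.
- Level per test: one-sided 0.025 for noninferiority and two-sided 0.05 for superiority (SAP 7.1). A false success in roxadustat's favour therefore has probability 0.025 for each of the three starred endpoints.
- Number of key secondary endpoints outside the sequence: 3 of 8 (SAP Tables 4 and 16).
- Correlation between the test statistics: not given in either document, so it is assumed over a range.

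**Step 1: reproduce the plan's figure.** In a fixed sequence, with all nulls true, a later test is reached only if the first one rejects. The error of the whole sequence is therefore that of a single test: 0.05 two-sided, or 0.025 in roxadustat's favour. Simulation with 400,000 draws of equally correlated normal statistics gave 0.0496 to 0.0509 two-sided for correlations from 0 to 0.9. The stated 0.05 is reproduced, but only for the tests inside the sequence.

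**Step 2: the three unsequenced endpoints.** If independent: 1 − (1 − 0.025)³ = 1 − 0.975³ = 0.0731. The bound under any dependence is 3 × 0.025 = 0.075.

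**Step 3: the sequence plus the three.** The sequence contributes one further term of 0.025. If independent: 1 − 0.975⁴ = 0.0963. The bound is 4 × 0.025 = 0.10.

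**Step 4: allow for correlation.** Chance of at least one false success in roxadustat's favour, all nulls true (the correlated columns are simulated):

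| | Independent | 0.3 | 0.6 | 0.9 | Bound |
|---|---|---|---|---|---|
| Three unsequenced endpoints | 7.3% | 6.9% | 5.9% | 4.2% | 7.5% |
| Sequence plus the three | 9.6% | 8.8% | 7.2% | 4.7% | 10% |
| All eight in one sequence | 2.5% | 2.5% | 2.5% | 2.5% | 2.5% |

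**Step 5: partial repair.** If MAP and hypertension return to the sequence and eGFR slope stays outside with its declaration rule, the figure is 1 − 0.975² = 0.0494, with a bound of 2 × 0.025 = 0.05.

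**The case against.** The strongest reply is that the SAP hides nothing. It says that the last three endpoints are unadjusted, and a reader of the tables can discount them. Reporting blood pressure noninferiority outside an efficacy hierarchy is also a defensible design: both endpoints are evaluated over the Safety Emergent Period (SAP 6.1.2.6 and 6.1.2.7), and the protocol's amendment rationale assumes only that roxadustat is not worse than placebo on them. That stands as far as it goes. There is no concealment, and leaving these endpoints outside the sequence could be right. But it would have to match the protocol, and it does not fit with language that declares success.

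A second reply is that the SAP names protocol v2.0 as its base. This does not explain the difference. The superseded table shown in the protocol's Attachment 1 also had both MAP (then as a superiority test) and hypertension inside the sequence.

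Three stronger readings are tempting, and the documents do not support them:
- A reader might infer that these three claims have no type I error control at all. SAP 7.1 gives each test its nominal level; only the multiplicity control is absent.
- A reader might infer that the SAP plainly allows these claims even if the EU primary fails. Section 7.4.2 still makes key secondary testing conditional on rejecting the EU primary hypothesis, and 7.4.2.6 and 7.4.2.7 contain wording that places blood pressure tests in the sequence. The SAP is contradictory rather than settled.
- A reader might compute 1 − 0.95 × 0.975³ = 11.9% and set it against 5%. That mixes a two-sided 5% for the sequence with one-sided 2.5% terms for the others. Moreover, the SAP footnote means that 5% is not claimed for all eight endpoints.

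Independence is also unlikely for MAP and hypertension, which come from the same visit-averaged readings. The independent figures therefore lie towards the upper end of the range.

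**Conclusion.** Wrong as written. The protocol and the SAP set incompatible conditions for the MAP and hypertension noninferiority claims, the SAP contradicts itself on the same point, and three of eight key secondary endpoints carry success rules without familywise control. The chance of at least one false success in roxadustat's favour is 4.2% to 7.3% for the three endpoints over assumed correlations of 0.9 down to 0. For the sequence plus the three it is 4.7% to 9.6%. The comparison is 2.5% when all eight are sequenced. These figures assume that every null is true (for noninferiority, a true effect at the margin), equal correlation among the statistics, and one-sided 0.025 for each claim.

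Error control for the EU primary and tests 1 to 5 is unaffected. The matter should be resolved, but it does not threaten the primary conclusion.

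**What to change.** Choose one of two routes.

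**(a) Restore the sequence.** In SAP Table 16 make MAP and hypertension noninferiority tests 6 and 7, as in protocol Table 9. Place eGFR slope after them, or report it as a nominal estimate with its confidence interval. Delete the footnotes to Tables 4 and 16 and the sentence on no adjustment, keeping them for eGFR slope alone if it is nominal. Placed last, these tests take no alpha from tests 1 to 5.

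**(b) Keep all three outside.** In SAP 7.4.2.6 to 7.4.2.8 replace the rules for concluding or declaring success with nominal estimates and confidence intervals, and amend protocol Table 9 to match.

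Under either route:
- remove from SAP 7.4.2.7 the statement that hypertension superiority is tested within the sequence;
- reconcile the noninferiority wording in 7.4.2 and the reference to the sequence in 7.4.2.6;
- enter the change and its rationale in the revision history.

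SAP section 1 allows revisions until database hard lock.

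**Cost.** This is a change of wording only; no data collection or sample size is affected. Under (a) there is no formal claim on blood pressure, or on eGFR slope if it is sequenced, when an earlier test fails. For blood pressure that is already the protocol's rule. Under (b) there is no formal claim on any of the three.
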